### 6.2 *Extension Period*

Unless contraindicated in the opinion of the investigator, after 8 weeks of study treatment, patients will enter an 18-week extension period (EP) in which they continue study treatment while their concomitant medications to treat pericarditis will be weaned, as described in Section 6.6.

### 6.3 *Follow-up Procedures*

At every assessment before study drug dose increase the patient will be re-evaluated. This includes ECG monitoring at approximately 5 hours post-morning dose ( $T_{max}$ ) to surveil for deleterious effects on ECG intervals (particularly the QTc interval) and rhythm.

Drug titration will be dependent on investigator or designate interrogation of the ECGs and the absence of abnormalities on those ECGs.

Vital signs, blood chemistry including liver function tests, hematology as well as INR assessments will be carried out at selected visits. Concurrent medications and (S)AEs will be recorded at all visits.

Final efficacy assessments will take place after 26 weeks of study treatment and include a clinical assessment, vital signs, Pain score NRS, a 12-lead ECG, the C-SSRS, as well as laboratory assessments.

For patients who do not enter the EP, final assessments will be done after 8 weeks, i.e. at Visit 5.

## **6.4 Study Medication**

CardiolRx™ (cannabidiol) solution contains cannabidiol at a concentration of 100 mg/mL. Inactive ingredients include medium-chain triglyceride (MCT) oil and Vitamin E.

## **6.5 Premature Interruption or Withdrawal from Study Treatment**

Before a decision is taken on premature discontinuation of study treatment, the medical monitor should be contacted.

### **6.5.1 Permanent Suspension of Study Treatment**

Permanent suspension of study treatment must occur in the following cases:

- If, in the view of the investigator, the patient experiences a severe allergic reaction that cannot be explained by the administration of any other medication.
- Development of liver function abnormality, as described in Section 9.2.11.3.
- Development of an AE or any medical condition, which, in the opinion of the investigator, necessitates permanent suspension of study treatment.
- If the patient did not tolerate the starting dose of 5 mg/kg of body weight b.i.d.
- Withdrawal of consent.

Patients have the right to discontinue study treatment for any reason. However, unless they withdraw consent and are no longer willing to participate, they should be followed for the remainder of the trial and all AEs should be reported, regardless of whether or not the event occurs under the care of another physician or institution.

### **6.5.2 Temporary Suspension of Treatment**

Temporary suspension of study treatment (up to 7 days) can occur in case of a development of an (S)AE or a medical condition, which, in the opinion of the investigator, necessitates temporary interruption of study treatment.

After temporary interruption of study treatment, all efforts should be made to re-institute study treatment using the last tolerated dose as soon as the clinical condition of the patient has stabilized.

### **6.5.3 Withdrawal of Consent**

Patients may decide to fully or partially withdraw their consent to participate in the study. At that point, it should be established, whether the withdrawal is related to study treatment, further assessments, or any further involvement in the study. If the withdrawal is primarily related to study treatment or specific assessments, patients should be encouraged to continue follow-up and to attend all other subsequent study assessments. Reports of AEs and SAEs should be collected until completion of the study for all withdrawals, unless the patient objects to such follow-up.

## **6.6 Concomitant Treatments**

Patients must be on SOC treatments for pericarditis with either NSAIDs, colchicine, or corticosteroids (in any combination) for at least 72 hours prior to Day 1. Unless contraindicated, these SOC treatments will be weaned during the 18 weeks EP as follows:

NSAIDs will be weaned within 2 weeks after the EP entry and corticosteroids within 6 weeks of EP entry (by 5 mg prednisone or equivalent every week).

For patients not taking corticosteroids, colchicine will be weaned between 2 and 4 weeks of EP entry, and for those on corticosteroids, colchicine weaning will be between 6 and 8 weeks of EP entry. Should it become evident that weaning of colchicine leads to high levels of pericarditis recurrence, the study leadership and the sponsor may decide colchicine weaning will no longer be performed during the EP.

Patients will not be allowed to be on immunosuppressive therapy with rilonacept, anakinra, canakinumab, methotrexate, azathioprine, cyclosporine, mycophenolate and/or IVIG and cannot take any cannabinoids during the study period nor strong inducers of CYP3A4 and CYP2C19 (see Section 17.7).

Use of digoxin and/or type 1 or 3 antiarrhythmics is an exclusion criterion for the trial. No drugs that are known to prolong QTc intervals should be started during the study (Appendix 17.6).

Also, because CardiolRx™ is known to inhibit the metabolism of certain other drugs, new symptoms or findings may represent toxicity from a concomitant medication that

had previously been well tolerated. Please refer to Section 6.3 of the Investigator Brochure (IB) and to Appendix 17.8.

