### **3.4 Current Treatment Options**

Currently, there are no US treatment guidelines for pericarditis or recurrent pericarditis; standard therapy consists of NSAIDs or aspirin with or without colchicine. Corticosteroids and other off-label immunosuppressants are used in patients with continued recurrence and inadequate response to conventional therapy.(Lotriente et al. 2010) European guidelines indicate that corticosteroids should generally be avoided, as their use has been associated with increased risk of recurrence, particularly if the dose is tapered rapidly. In the most severe cases, pericardectomy may be performed, although it does not always prevent recurrence. Among the patients with recurrent pericarditis with multiple recurrences and/or complications, disease burden is substantial and treatment options are currently inadequate.(Adler et al. 2015)

The potential of IL-1 inhibition was evaluated in a trial of the recombinant IL-1-receptor antagonist anakinra in a small number of patients with colchicine-resistant idiopathic recurrent pericarditis who had previously had pericarditis recurrence after the withdrawal of glucocorticoids; many of the patients continued using colchicine during that trial.(Brucato et al. 2016) A subsequent phase 2 trial of rilonacept, an IL-1 $\alpha$  and IL-1 $\beta$  cytokine trap (A. L. Klein, Lin, et al. 2021), provided early evidence of resolution of

pericardial inflammation. The phase 3 trial RHAPSODY was then conducted to test the primary hypothesis that rilonacept would lead to a lower risk of pericarditis recurrence than placebo. The trial found that among the patients with recurrent pericarditis, rilonacept led to rapid resolution of recurrent pericarditis episodes and to a significantly lower risk of pericarditis recurrence than placebo after withdrawal of background therapy.(A. L. Klein, Imazio, et al. 2021) The only approved therapy for the treatment of recurrent pericarditis is rilonacept.

The clinical benefit seen with IL-1 inhibitors is hypothesized to be indirect evidence of the involvement of the NLRP3 inflammasome signaling in the pathophysiology of pericarditis.(Mauro et al. 2021)

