### 5.2 *Inclusion Criteria*

The following inclusion criteria must be met to enroll a patient into this study:

1. Male or female 18 years of age or older
2. Diagnosis of at least two episodes of recurrent pericarditis\*,  
3. At least 1 day with pericarditis pain  $\geq 4$  on the 11-point NRS within prior 7 days
4. One of:
  - a. CRP\*\* level  $\geq 1.0$  mg/dL within prior 7 days **OR**
  - b. Evidence of pericardial inflammation assessed by delayed pericardial hyperenhancement on CMR
5. Currently receiving NSAIDs and/or colchicine and/or corticosteroids for treatment of pericarditis (in any combination) in stable doses
6. Male patients with partners of childbearing potential who have had a vasectomy or are willing to use double barrier contraception methods during the conduct of the study and for 2 months after the last dose of study drug.
7. Women of childbearing potential willing to use an acceptable method of contraception starting with study drug administration and for a minimum of 2 months after study completion. Otherwise, women must be postmenopausal (at least 1 year absence of vaginal bleeding or spotting and confirmed by follicle stimulating hormone [FSH]  $\geq 40$  mIU/mL [or  $\geq 40$  IU/L] if less than 2 years postmenopausal) or be surgically sterile.

\* Diagnosis of pericarditis according to the 2015 ESC Guidelines for the Diagnosis and Management of Pericardial Diseases (Adler et al. 2015):

At least two of:

- a. Pericarditic chest pain
- b. Pericardial rub
- c. New widespread ST-segment elevation or PR-segment depression according to ECG findings
- d. Pericardial effusion (new or worsening)

\*\* Conversion: 1 mg/dL CRP = 10 mg/L hs-CRP

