### **5.3 Exclusion Criteria**

Patients meeting any of the following criteria will be excluded from the study:

1. Diagnosis of pericarditis that is secondary to specific prohibited etiologies, including tuberculosis (TB); neoplastic, purulent, or radiation etiologies; post-thoracic blunt trauma (e.g., motor vehicle accident); myocarditis
2. Estimated glomerular filtration rate (eGFR) <30 mL/min
3. Elevated alanine aminotransferase (ALT) or aspartate aminotransferase (AST) > 5 times the upper limit of normal (ULN) or ALT or AST >3x ULN plus bilirubin >2x ULN
4. Sepsis, defined as documented bacteremia at the time of screening or other documented active infection
5. Prior history of sustained ventricular arrhythmias
6. History of QT interval prolongation
7. QTc interval > 500 msec (please refer to Section 9.2.3 for bundle branch block, bifascicular block and paced rhythm correction)
8. Current participation in any research study involving investigational drugs or device
9. Inability or unwillingness to give informed consent
10. Ongoing drug or alcohol abuse
11. On any cannabinoid during the past month
12. Women who are pregnant or breastfeeding
13. Current diagnosis of cancer, with the exception of non-melanoma skin cancer
14. Any factor, which would make it unlikely that the patient can comply with the study procedures
15. Showing suicidal tendency as per the C-SSRS, administered at screening
16. On digoxin and/or type 1 or 3 antiarrhythmics
17. On immunosuppressive therapy with any of the following:
  - a. Rilonacept
  - b. Anakinra
  - c. Canakinumab
  - d. Methotrexate
  - e. Azathioprine
  - f. Cyclosporine
  - g. IVIG

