#### Visit 5 (Week 8 ± 4 days) – final study visits for patients not continuing in the EP

The following evaluations will be performed at 8 weeks after start of study medication:

- Clinical assessment
- Vital signs, including HR, blood pressure and body weight
- Review/collection of daily diary NRS pain scores, if not submitted electronically to Patient Portal if the patient has completed the questionnaire on paper
- Collect highest NRS pain score within the past 7 days
- 12-lead ECG 5 hours post morning dose (time window 3.5 – 6 hours); QTc intervals on ECG to be reviewed by site investigator, or designate, who decides if patient can continue study medication
- C-SSRS
- Study drug accountability
- Recording of changes in concomitant medications
- Start weaning background therapy over the next 8 weeks for patients continuing in the EP
- AE and SAE recording
- Local laboratory assessments, including CRP, CBC, AST/ALT, alkaline phosphatase, bilirubin, creatinine/eGFR, INR

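### The steroid weaning step and the 6-week deadline in Protocol 6.6 agree only up to 30 mg (35 mg with a step at entry); no dose limit applies and no text says which governs

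*Protocol*

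**What the plan says.** Protocol Section 6.6 introduces the weaning schedule with "Unless contraindicated, these SOC treatments will be weaned during the 18 weeks EP as follows". For steroids it then has "corticosteroids within 6 weeks of EP entry (by 5 mg prednisone or equivalent every week". The next rule is that "for those on corticosteroids, colchicine weaning will be between 6 and 8 weeks of EP entry". In Section 9.1, the Visit 5 list gives one overall period: "Start weaning background therapy over the next 8 weeks for patients continuing in the EP".

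On who can be in this position, inclusion criterion 5 (Section 5.2) reads "Currently receiving NSAIDs and/or colchicine and/or corticosteroids for treatment of pericarditis (in any combination) in stable doses", with no maximum dose. Exclusion criterion 17 (Section 5.3), "On immunosuppressive therapy with any of the following", names seven agents, and corticosteroids are not among them. Section 6.2 lets patients into the EP unless the investigator sees a contraindication; steroid dose is not mentioned. SAP Sections 4.1 and 4.2 repeat the eligibility criteria without adding a limit.

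On analysis, SAP Section 8.5.2 takes EP recurrence from a coded adverse event and reports it in Table 21. SAP Section 8.3.5 summarizes medications at the second ATC level, and Listing 4 lists them by patient. No planned table shows steroid dose at EP entry or whether weaning was completed.

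**The concern.** A fixed weekly step and a fixed number of weeks together determine the total dose that can be removed. A patient who enters the EP above that total cannot be weaned as written, and the protocol does not say which part gives way. Sites would settle it case by case.

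This bears on what the extension is for. Section 3.5 gives as a purpose of the pilot whether background therapy, corticosteroids included, can be weaned, and says the results will inform a randomized withdrawal trial. Recurrence during the EP is a listed efficacy endpoint (Section 4.1.3). The protocol's own background makes the choice relevant to that endpoint. On corticosteroids, Section 3.4 says "their use has been associated with increased risk of recurrence, particularly if the dose is tapered rapidly", and Section 3.5 says relapse on reducing or stopping steroids is frequent, more so without colchicine alongside. A site that keeps the deadline tapers faster than the stated step. A site that keeps the step leaves less time off steroid and may withdraw colchicine during the taper. For such patients the recurrence result partly reflects which limit the site kept, and the planned tables would not show it.

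**Working it through.** The documents state no dose ceiling, so there is no figure to reproduce. The check is direct arithmetic.

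**Inputs**
- Step: 5 mg per week (Section 6.6).
- Steroid deadline: EP week 6 (Section 6.6).
- Colchicine window for patients on steroid: EP weeks 6 to 8 (Section 6.6).
- Overall weaning period: 8 weeks (Visit 5).
- EP length: 18 weeks (Section 6.2).

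Two ways of counting are allowed: (A) first reduction one week after EP entry; (B) first reduction on the day of EP entry.

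**Largest dose that can be stopped = step × number of steps**
- By week 6: (A) 6 × 5 = 30 mg; (B) 7 × 5 = 35 mg.
- By week 8: (A) 8 × 5 = 40 mg; (B) 9 × 5 = 45 mg.
- By week 18, counting (A): 18 × 5 = 90 mg.

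**Consequences by dose at EP entry.** Steps = dose ÷ 5. Dose left at week 6 = dose − 30 (A) or dose − 35 (B), not below zero. The last column is dose ÷ 6, the equal weekly step that would stop the steroid in six steps. Every dose in the table is an illustrative assumption.

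| Dose at EP entry | Steps | Off at EP week (A / B) | Left at week 6 (A / B) | Step needed to meet 6 weeks |
|---|---|---|---|---|
| 30 mg | 6 | 6 / 5 | 0 / 0 mg | 5.0 mg |
| 35 mg | 7 | 7 / 6 | 5 / 0 mg | 5.8 mg |
| 40 mg | 8 | 8 / 7 | 10 / 5 mg | 6.7 mg |
| 50 mg | 10 | 10 / 9 | 20 / 15 mg | 8.3 mg |
| 60 mg | 12 | 12 / 11 | 30 / 25 mg | 10.0 mg |

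**Time off steroid within the EP, counting (A).** A 60 mg patient kept to the step has 18 − 12 = 6 weeks off steroid. The same patient kept to the deadline has 18 − 6 = 12 weeks, at twice the stated step (10 ÷ 5 = 2).

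**Which limits fail, and when**
- Up to 30 mg (35 mg under B), step and deadline are compatible.
- Above that, and up to 40 mg (45 mg under B), keeping the step misses the 6-week deadline but stays inside the 8-week total.
- Above 40 mg (45 mg), keeping the step also exceeds the 8-week total.
- The colchicine overlap arises only for patients taking both drugs.

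**The case against.** The strongest reply is that the conflict may seldom occur. Section 3.5 says steroids for pericarditis are usually given at low to moderate doses, and at 30 mg or below nothing is wrong. That stands as a limit on reach. It is background text without a mg figure, though, and sets no eligibility limit.

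The protocol also allows flexibility. Weaning and EP entry are both subject to contraindication, and Section 14.4.1 provides for deviations in the patient's interest to be agreed and logged. These provisions decide whether to wean, or how to record a departure. They do not say whether step or deadline governs, and the same section asks for instructions to be followed exactly.

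The deadline might be read as the time by which weaning starts. A colchicine window that opens at week 6 and an 8-week overall total both fit completion by week 6 better. That is an inference, because Section 6.6 gives calendar windows and does not state that colchicine must wait for the steroid.

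Finally, this is a single-arm pilot of about 25 patients with descriptive analysis only, and recurrence is an additional endpoint. That limits the damage. But describing how weaning went is a purpose of the extension, so the description should be interpretable.

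**Conclusion.** The point holds, conditionally on dose. Section 6.6 cannot be followed as written for an eligible patient above 30 mg at EP entry (35 mg with a step on the day of entry). The arithmetic is certain. The number of patients affected is not known: the documents give no dose distribution and do not say whether steroid dose is held constant from Day 1 to Week 8.

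A reader might infer more than the documents support:
- That the rule contradicts itself for every steroid patient. It does not at or below 30 mg.
- That any overrun of 6 weeks also breaks the Visit 5 total. That needs more than 40 mg (45 mg).
- That the taper cannot fit in the extension. At the stated step, doses up to 90 mg finish within 18 weeks.
- That a given share of the recurrence percentage is compromised. No count of such patients can be derived. Planned enrolment is also not the number entering the EP, and the SAP does not state the denominator for this endpoint.
- That the primary endpoint is affected. It is measured at Week 8, when weaning only begins.

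What is affected is the weaning-feasibility aim and the EP recurrence percentage, to an extent that depends on how many patients enter the EP above the threshold.

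**What to change.** **Protocol.** Reconcile the weekly step, the 6-week limit, the colchicine window (all Section 6.6) and the 8-week total (Visit 5) so that they are compatible for every eligible steroid dose at EP entry. State which governs if they conflict, and how the colchicine window applies to a patient whose steroid is not finished. The clinical choice is the sponsor's.

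**SAP.** Alongside Table 21, among patients on corticosteroids at EP entry, report:
- the number off steroid by the scheduled time;
- the last date of the background steroid course, from recorded medication stop dates, with incomplete dates shown as unknown and steroids given as rescue under Section 6.7 counted separately;
- the prednisone-equivalent dose at EP entry, if dose is captured in the eCRF.

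**Cost.** A short wording amendment and a small descriptive display, with no added visits. Section 9.2.8 requires changes in concomitant medication to be recorded and the SAP uses start and stop dates, so the first two items should be available. The documents do not confirm that steroid dose is captured, so the third may not be. The SAP describes eligibility and dosing in the past tense and reports patients already enrolled, so an amendment may come too late for some of them; the SAP display is useful either way.

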## **6.7 Management of Pericarditis Recurrence During the Extension Period**

Pericarditis recurrence during the extension period is defined as the recurrence of typical pericarditis pain associated with supportive objective evidence of pericarditis in the opinion of the investigator. At any timepoint during the EP, patients who experience suspected recurrence of their pericarditis will have been instructed to inform their site Investigator as soon as possible. Patients who experience a suspected recurrence of pericarditis symptoms will be requested to report to the study site/clinic for a scheduled or unscheduled visit, during which clinical assessments will be performed to gather all the necessary diagnostic data to confirm or rule out the presence of pericarditis recurrence. The Investigator will evaluate all assessments performed for a diagnostic workup, whether at the study site or at locations outside.

Following communication with the study medical monitor, patients who report at least 1 day with pericarditis pain measurement  $\geq 4$  on the 11-point NRS **AND** have a CRP value  $\geq 1$  mg/dL (either on the same day or separated by no more than 7 days) during the EP of the trial will receive rescue therapy at the discretion of the investigator, i.e., if not already taking; analgesics first, then NSAIDs, and then colchicine. Immunosuppressive therapy such as corticosteroids or rilonacept may be added for pericarditis recurrence at the discretion of the investigator.

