5 ANALYSIS POPULATIONS

5.1 Full analysis set (FAS)

All patients who were enrolled and who started the IMP will be included in the Full Analysis set.

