8.5 Efficacy analysis

Given the small sample size and the design of the study, no inferential statistical analyses are planned. All data collected during a scheduled visit (except the NRS score which was collected daily) will be included in the descriptive statistics.

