8.5.2 Additional efficacy analysis

- The change in patient-reported pericarditis pain using an 11-point NRS from baseline to 26 weeks will be summarized as a continuous variable.
- The change in patient-reported pericarditis pain using an 11-point NRS from baseline to other intermediate weeks (i.e. visits 3,4,5,6,7) will be summarized as a continuous variable.
- Patients with normalized CRP levels (i.e with a CRP \leq 0.5 mg/dL) at 8 weeks (for patients with CRP \geq 1.0 mg/dL at baseline) will be summarized as a categorical variable
- Patients with normalized CRP levels (i.e with a CRP \leq 0.5 mg/dL) at 26 weeks (for patients with CRP \geq 1.0 mg/dL at baseline) will be summarized as a categorical variable
- Patients with pericarditis recurrence during the extension period (EP), i.e with an adverse event occurring between week 8 and week 26 and coded with the following LLT code 10087207 (Recurrent pericarditis) will be summarized as a categorical variable

- Time to CRP normalization (in days) (i.e time between IMP start date up to the first blood draw date when $CRP \leq 0.5 \text{ mg/dL}$) for patients with $CRP \geq 1.0 \text{ mg/dL}$ at baseline will be summarized as a continuous variable. If CRP had not normalized at the timepoint assessed (i.e 8 week visit date (for SSA) or 26 weeks visit date for the final analysis), the patients concerned will not be included in the analysis for this outcome.
- CRP change from baseline at 26 weeks (%) will be summarized as a continuous variable.

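### The SAP has no rule for rescue after an extension-period recurrence, so Week-26 CRP normalization can credit CardiolRx with a result obtained after rilonacept, corticosteroid or other anti-inflammatory rescue

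*Protocol*

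**What the plan says.** **Rescue.** Protocol 6.7 covers recurrence during the extension period only. A patient with an NRS score of at least 4 on one day and a CRP of at least 1 mg/dL, no more than 7 days apart, receives rescue: analgesics, then NSAIDs, then colchicine, where not already taken. It adds: "Immunosuppressive therapy such as corticosteroids or rilonacept may be added for pericarditis recurrence at the discretion of the investigator".

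**General medication rule.** Protocol 6.6, the section just before, says "Patients will not be allowed to be on immunosuppressive therapy with rilonacept, anakinra, canakinumab, methotrexate" and other named agents, with no exception stated. The synopsis says the same. Use at entry is dealt with separately in exclusion criterion 17 ("On immunosuppressive therapy with any of the following").

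**Who stays in the data.** Starting rescue is not among the reasons in Protocol 6.5.1 that force study drug to stop. Patients who do stop are still followed unless they withdraw consent: "they should be followed for the remainder of the trial and all AEs should be reported". SAP 5.1 says: "All patients who were enrolled and who started the IMP will be included in the Full Analysis set".

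**What is summarized.** SAP 8.5 says: "All data collected during a scheduled visit (except the NRS score which was collected daily) will be included in the descriptive statistics". SAP 8.5.2 defines normalization as a CRP of 0.5 mg/dL or lower, in patients who had at least 1.0 mg/dL at baseline. Time to normalization is the "time between IMP start date up to the first blood draw date when" CRP first meets that threshold, with the cut-off at the "26 weeks visit date for the final analysis". Patients who have not normalized by then are left out of that summary. Neither section mentions rescue.

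**The concern.** The question is what a Week-26 result can be attributed to. Protocol 3.4 reports that rilonacept resolved recurrent episodes rapidly. A patient who meets the CRP trigger in Protocol 6.7 is, at that moment, above the SAP's normalization threshold (at least 1 mg/dL against 0.5 mg/dL or lower). If that patient's Week-26 CRP is 0.5 mg/dL or lower, the fall came after the recurrence and most likely after rescue had started. The SAP still counts the patient as normalized, and there is no control arm in which the same thing would show up.

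This bears on the purpose of the extension period. Protocol 3.5 says the pilot is to assess whether background therapy can be weaned on CardiolRx, and to inform a randomized withdrawal trial. A patient who was weaned, recurred, was rescued and then had a low CRP has not shown that weaning worked, but would count as a favourable Week-26 CRP result.

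**Working it through.** The plan gives no figure for this point, so there is nothing to reproduce. The check classifies the endpoints and then asks what can be sized.

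**1. Which additional endpoints can contain post-rescue values?** Rescue under Protocol 6.7 starts only in the extension period, which follows the Week-8 visit. The six endpoints are those in Protocol 4.1.3 and SAP 2.3.2.

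| Endpoint | Can include post-rescue values? |
|---|---|
| NRS change at Week 26 (Table 17) | Yes |
| CRP normalized at Week 8 (Table 18) | No, precedes the extension period |
| Recurrence during the extension period (Table 21) | No, the event precedes its rescue |
| CRP normalized at Week 26 (Table 18) | Yes |
| Time to CRP normalization, final analysis (Table 19) | Yes, if first normalization follows rescue |
| CRP % change at Week 26 (Table 20) | Yes |

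The count is 4 of 6. The primary endpoint, NRS change at Week 8, is not affected.

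**2. Which CRP draws are exposed?** SAP Table 4-1 schedules post-baseline CRP at Weeks 3, 8, 16 and 26. Weeks 16 and 26 fall in the extension period, so 2 of 4 draws can follow rescue.

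**3. What is one patient worth in Table 18?** With m patients in the Week-26 denominator, moving one from normalized to not normalized changes the percentage by 100/m points. The documents do not give m, so these values are assumed:
- m = 25: 100/25 = 4.0 points
- m = 15: 100/15 = 6.7 points
- m = 10: 100/10 = 10.0 points

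Planned enrolment is about 25, and only patients with baseline CRP of at least 1.0 mg/dL are counted. Patients can also enter on CMR evidence, so m may be well below 25.

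**4. Should post-rescue normalizations be removed from Table 19?** SAP 8.5.2 already drops patients who do not normalize, so leaving out post-rescue normalizations would delete those patients. Their times come from the Week-16 or Week-26 draws, the latest ones available. Illustration, with assumed values: nine patients normalize at day 21 and one, after rescue, at day 112.
- All data: (9 × 21 + 112)/10 = 301/10 = 30.1 days
- Rescued patient removed: (9 × 21)/9 = 21.0 days

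Removal makes the drug look faster, so Table 19 should keep these values and disclose them.

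**5. What cannot be computed?** The number of rescued patients and the resulting shift. The documents give no extension-period recurrence rate on CardiolRx, no share given each rescue drug, and no count with baseline CRP of at least 1.0 mg/dL. Protocol 3.1 cites further episodes in 20% to 40% of patients with two or more recurrences, but without a time window and not on this drug, so I do not use it here.

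**The case against.** The strongest reply is that including all data is a legitimate choice. It amounts to a treatment-policy summary, in a descriptive pilot of about 25 patients with no inference planned, for outcomes the protocol lists as additional parameters of interest. Failure in the extension period has its own endpoint in Table 21. Listings 4 and 5 let a reader identify rescued patients, and SAP 8.5.3 plans to relate pericarditis medication to NRS scores.

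Much of this stands. The all-data result should be kept, and recurrence is the endpoint closest to the planned withdrawal trial. Time to normalization is affected only in a patient with raised baseline CRP who had not normalized before rescue and did so afterwards. But the SAP does not say that it has chosen a treatment-policy summary, and none of these outputs changes Table 18. The medication analysis covers NRS, not CRP.

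A reader might also infer that Protocol 6.6 and 6.7 contradict each other on rilonacept. The documents do not support more than a missing cross-reference. Section 6.7 directly follows 6.6, is limited by its heading to extension-period recurrence, and names rilonacept. The specific provision can reasonably be read as the exception to the general rule.

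**Conclusion.** The gap is real, limited, and worth closing before the final analysis. The SAP has no handling of rescue, so Week-26 CRP normalization can include patients whose CRP fell after anti-inflammatory rescue. Three other Week-26 or final-analysis outcomes can contain post-rescue values too. This is a statement of what can happen: it takes at least one rescued patient with a contributing value. At an assumed denominator of 10 to 25, each such patient counted as normalized is worth 10 to 4 percentage points in Table 18.

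Two stronger readings are not supported. One is that the main efficacy result is compromised: the primary endpoint and the staged Week-8 analysis precede any rescue under Protocol 6.7. The other is that the Week-26 results will be inflated by a known amount: the inputs for that are absent.

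The conclusion rests on the SAP text available for review. Part of SAP Section 7 was not available, but that section concerns the Week-8 staged analysis and is unlikely to hold a rescue rule.

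**What to change.** **SAP 8.5.2 and Table 18.** Keep the all-data Week-26 percentage and add a row beside it, defined along these lines: *Patients who, before the Week-26 visit, started or increased an NSAID, colchicine, a corticosteroid or rilonacept for a pericarditis recurrence under Protocol 6.7 are counted as not normalized.* NSAIDs and colchicine belong in the definition because Protocol 6.7 lists them as rescue. Print the denominator of each row, since SAP 9.3 drops missing values from percentages.

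**Tables 17, 19 and 20.** Add a footnote giving the number of contributing values that follow such rescue. Do not remove post-rescue normalizers from Table 19, for the reason shown in step 4. Replacing Week-26 change scores would need imputed values, and Protocol 11.4 plans none.

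**Protocol 6.6 and synopsis (optional, minor).** After the list of barred agents, add: *except as permitted in Section 6.7*. The clause should not name rilonacept alone, because the immunosuppressants in 6.7 are given as examples.

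**Cost.** One extra derivation, a few footnotes, and a possibly lower Week-26 percentage in the added row. No new data are needed: Protocol 9.2.8 requires medication changes to be recorded, SAP 8.3.5 codes them taking indication into account, and Listing 4 shows them.
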